NCT03679975

A Single Center Study to Evaluate the Effect of Riluzole Oral Soluble Film on Swallowing Safety
in Individuals With Amyotrophic Lateral Sclerosis

Protocol
18-Oct-2017

A Single Center Study to Evaluate the Effect of Riluzole Oral Soluble Film on Swallowing Safety in Individuals With Amyotrophic Lateral Sclerosis

Amendment 1

Summary of Changes from Version 1.0 (July 27, 2017) to Version 2.0 (October 18, 2017)

Note:

Major changes described in the following table have been made in this document to address the following issues:

- **Additional exclusion added to clarify the exclusion for the PAS score applies to any previous swallowing studies**
- **Additional exclusion added for subjects with a history of two or more episodes of aspiration pneumonia requiring hospitalization**
- **Modified hepatic function exclusion requirement for subjects currently on Riluzole**
- **Modified hepatic function exclusion requirement for subjects receiving Riluzole for the first time**
- **Added description of comprehensive and brief physical examinations and comprehensive neurological and brief neurological examinations**

Few minor changes involving wordsmithing for clarity and consistency, punctuation, and correction of typos have also been made but are not included in this table because they are not substantive changes. However, they are visible in the tracked-changes version of the protocol

CONFIDENTIAL INFORMATION

The information in this study protocol is confidential. Any disclosure, copying or distribution of the information contained within is strictly prohibited without written consent from MonoSol Rx LLC.

Section	Version No 1.0 July 27, 2017	Amendment 1 (Version 2.0) October 18, 2017	Rationale
3. Synopsis – Exclusion Criteria		
p 7
 
2. Subjects with a prior swallowing study that has shown a PAS of 3 or greater
 
3. Subjects with a history of two or more episodes of aspiration pneumonia requiring hospitalization
	Additional exclusions added in response to Information Request (IR) - IND 130939-Comments on new protocol submission/SN0003_24_August_2017
3. Synopsis – Exclusion Criteria	
p 7
 
8. Subjects with hepatic impairment as defined by baseline elevations of serum aminotransferases greater than 5 times upper limit of normal or evidence of liver dysfunction (e.g., elevated bilirubin).
	
p 7
 
10. Subjects currently taking riluzole with ALT levels greater than 5 times upper limit of normal or with evidence of clinical jaundice. (Riluzole should be discontinued in these patients).
	Changed to be consistent with the Reference Listed Drug (RLD), RILUTEK (NDA 020599) label
3. Synopsis – Exclusion Criteria		
P 7
 
11. Subjects who will be receiving riluzole for the first time who exhibit baseline elevations of several LFTs (especially elevated bilirubin). (These findings at baseline should preclude the use of riluzole including ROSF.).
	Added to be consistent with the Reference Listed Drug (RLD), RILUTEK (NDA 020599) label
8.1.2 Exclusion		
p 18
 
2. Subjects with a prior
	Additional exclusions added in response to Information Request (IR) - IND

CONFIDENTIAL INFORMATION

The information in this study protocol is confidential. Any disclosure, copying or distribution of the information contained within is strictly prohibited without written consent from MonoSol Rx LLC.

Section	Version No 1.0 July 27, 2017	Amendment 1 (Version 2.0) October 18, 2017	Rationale
Criteria		swallowing study that has shown a PAS of 3 or greater 3. Subjects with a history of two or more episodes of aspiration pneumonia requiring hospitalization	130939-Comments on new protocol submission/SN0003_24_August_2017
8.1.2 Exclusion Criteria	P 19 8. Subjects with hepatic impairment as defined by baseline elevations of serum aminotransferases greater than 5 times upper limit of normal or evidence of liver dysfunction (e.g., elevated bilirubin).	P 19 10.. Subjects currently taking riluzole with ALT levels greater than 5 times upper limit of normal or with evidence of clinical jaundice. (Riluzole should be discontinued in these patients .)	Changed to be consistent with the Reference Listed Drug (RLD), RILUTEK (NDA 020599) label
8.1.2 Exclusion Criteria		P 19 11. Subjects who will be receiving riluzole for the first time who exhibit baseline elevations of several LFTs (especially elevated bilirubin). (These findings at baseline should preclude the use of riluzole including ROSF.).	Added to be consistent with the Reference Listed Drug (RLD), RILUTEK (NDA 020599) label
10.2.2.1. Videofluor oscopy Swallow Study (VFSS 1- PAS)		P 27 The start time and finish time for the standardized bolus protocol will be recorded for both VFSS 1 and VFSS 2.	Added in response to Information Request (IR) - IND 130939-Comments on new protocol submission/SN0003_24_August_2017

CONFIDENTIAL INFORMATION

The information in this study protocol is confidential. Any disclosure, copying or distribution of the information contained within is strictly prohibited without written consent from MonoSol Rx LLC.

Section	Version No 1.0 July 27, 2017	Amendment 1 (Version 2.0) October 18, 2017	Rationale
10.2.2.1. Videofluor oscopy Swallow Study (VFSS 1- PAS)	P 26 Immediately following VFSS 1-PAS, the patient will then be administered ROSF on the dorsum of tongue along the median lingual sulcus.	P 28 ...sulcus, , and the time of administration will be recorded.	Added in response to Information Request (IR) - IND 130939-Comments on new protocol submission/SN0003_24_August_2017
10.2.2.1. Videofluor oscopy Swallow Study (VFSS 1- PAS)		P 28 The investigator should record whether or not ROSF is fully dissolved at 3 minutes after dosing. In the event that ROSF is not fully dissolved at 3 minutes, the investigator will record the time that it is confirmed that ROSF is fully dissolved.	Added in response to Information Request (IR) - IND 130939-Comments on new protocol submission/SN0003_24_August_2017
10.3.6. Clinical Assessments		P 30 Subjects will undergo a comprehensive physical and neurological examination at screening, and a brief physical and neurological examination at Visit 1 following the second VFSS. The comprehensive physical examination will include complete vital signs, weight, height, general appearance, and evaluation of systems: head, ears, eyes, nose, and throat; respiratory; abdomen; lymph nodes; spine; skin; cardiovascular; and	The CRO managing the protocol requested a description of the comprehensive and the brief physical exam and the neurological exam and brief neurological exam

CONFIDENTIAL INFORMATION

The information in this study protocol is confidential. Any disclosure, copying or distribution of the information contained within is strictly prohibited without written consent from MonoSol Rx LLC.

Section	Version No 1.0 July 27, 2017	Amendment 1 (Version 2.0) October 18, 2017	Rationale
		
extremities. The brief general physical examination will include abbreviated vital signs (blood pressure, heart rate, respiratory rate), and examination of the cardiovascular and respiratory systems and abdomen. Other elements may be included depending on symptoms or physical findings.
 
The comprehensive neurological examination will include (as permitted by the patient’s capabilities) cranial nerves 2-12, muscle tone and strength, tendon reflexes and plantar response, sensory function (pain, light touch, position, vibration), coordination (finger-nose), and gait. The brief neurological examination will include cranial nerves 2-12, muscle strength, tendon reflexes, plantar response, and sensory function (pain, light touch, position, vibration). Other elements may be included depending on symptoms or physical findings
	
10.3.12. Physical and Neurological Examination		
P 34
 
Subjects will undergo a comprehensive physical and neurological examination at screening, and a brief physical
	The CRO managing the protocol requested a description of the comprehensive and the brief physical exam and the neurological exam and brief

CONFIDENTIAL INFORMATION

The information in this study protocol is confidential. Any disclosure, copying or distribution of the information contained within is strictly prohibited without written consent from MonoSol Rx LLC.

Section	Version No 1.0 July 27, 2017	Amendment 1 (Version 2.0) October 18, 2017	Rationale

3. SYNOPSIS

Title	A single center study to evaluate the effect of Riluzole Oral Soluble Film (ROSF) on swallowing safety in individuals with amyotrophic lateral sclerosis.
Objectives	The primary objective is to evaluate the effect, if any, of a single 50 mg dose of Riluzole Oral Soluble Film (ROSF) on swallowing safety in individuals with amyotrophic lateral sclerosis.
Experimental Design	This is a single site, single dose, open-label safety study. Approximately thirty (30) individuals with amyotrophic lateral sclerosis (ALS) will be enrolled. Subjects seen in the ALS Clinic at the University of Florida will be screened to determine eligibility according to the specified inclusion/exclusion criteria. Following enrollment and informed consent, subjects will undergo a clinical evaluation including the validated Amyotrophic Lateral Sclerosis Functional Rating Scale-Revised (ALSFRS-R). Swallowing safety will be assessed using the gold standard Videofluoroscopic Swallowing Study to afford direct visualization of the swallowing process and any episodes of penetration or aspiration quantified using the validated Penetration Aspiration Scale (PAS). Subjects will undergo a standardized protocol that includes 12 bolus stimuli presentations of different liquid and food materials to test the swallow across a continuum of textures and materials. Immediately following, subjects will be given a single dose of riluzole oral soluble film (ROSF) 50mg, placed on the median lingual sulcus of the dorsum of the tongue. Three minutes after the administration of ROSF, the identical standardized VFSS protocol will be re-administered to allow a comparison of swallowing safety (using the PAS scale) pre vs. post ROSF administration.
Interventions	ROSF is a new formulation of riluzole 50mg that allows for rapid dissolution of the medication through a soluble film placed on the dorsum of the tongue along the median lingual sulcus.
Study Duration	The anticipated time from study enrollment until completion of data analyses is approximately 9 months.
Participant Duration:	Total study participant time is expected to be approximately 30 days from time of screening to completion of study.

CONFIDENTIAL INFORMATION

The information in this study protocol is confidential. Any disclosure, copying or distribution of the information contained within is strictly prohibited without written consent from MonoSol Rx LLC.

Study Population and Sample Size	
Approximately 30 subjects with ALS will be enrolled. The inclusion criteria are intended to provide a representative cohort of subjects with ALS who are currently on an oral diet and able to take foods and liquids by mouth, equivalent to a score of 3 or above on the Functional Oral Intake Scale (Crary, 2005). Inclusion will require a diagnosis of probable or definite ALS in accordance with the Revisited El-Escorial Criteria (Cedarbaum, 1999), a prescription to take riluzole at or before the time of the administration of study drug, no allergies or contraindications to barium, riluzole or inactive ingredients* in ROSF, and no contraindications to study procedures. Female subjects must not be pregnant or breast-feeding.
 
*See Investigator’s Brochure

Phase	2
Test Drug	Riluzole Oral Soluble Film 50 mg (MonoSol Rx, LLC)
Inclusion Criteria	
 1. Male or female subjects between 18-80 years of age, inclusive 2. Subjects have a diagnosis of probable or definite ALS in accordance with the Revisited El-Escorial Criteria (Cedarbaum, 1999) 3. Subjects must be currently on an oral diet and able to take foods and liquids by mouth equivalent to a score of 3 or above on the Functional Oral Intake Scale (Crary, 2005). 4. Subjects must have no known allergy to barium sulfate, riluzole or inactive ingredients* in ROSF. 5. Subjects or subject’s legally authorized representative must be willing and able to complete informed consent/assent and HIPAA authorization. 6. Ability to comprehend and be informed of the nature of the study, as assessed by the PI or Sub-Investigator. 7. Subjects prescribed to take riluzole at or before the time of first dosing. (The study is open to subjects currently taking riluzole at screening, subjects who are not currently taking riluzole at screening who have taken riluzole in the past, and subjects to be newly started on riluzole (given as ROSF in the course of

CONFIDENTIAL INFORMATION

The information in this study protocol is confidential. Any disclosure, copying or distribution of the information contained within is strictly prohibited without written consent from MonoSol Rx LLC.

	
this study).
 
 8. Availability to volunteer for the entire study duration and willing to adhere to all protocol requirements 9. Female subjects of childbearing potential must have a negative urine pregnancy test at Screening and Visit 1. Female subjects of childbearing potential (i.e. not surgically sterile, not 2 years postmenopausal, or not with a sterile partner) must have a negative pregnancy test at screening and Visit 1, agree to abstinence, practicing double barrier contraception or using an FDA approved barrier method contraceptive (e.g., licensed hormonal or barrier methods) for greater than 2 months prior to screening visit and commit to an acceptable form of birth control for the duration of the study and for 30 days after participation in the study. 
*See Investigator Brochure

Exclusion Criteria
	
 1. Subjects who score 2 or below on the Functional Oral Intake Scale (Crary, 2005) 2. Subjects with a prior swallowing study that has shown a PAS of 3 or greater 3. Subjects with a history of two or more episodes of aspiration pneumonia requiring hospitalization 4. Subjects with a history of clinically significant liver disease, renal disease, or any other medical condition judged to be exclusionary by the investigator 5. Subjects who are unwilling to sign informed consent or subjects who for any other reason in the judgment of investigator are unable to complete the study 6. Female subjects who have a positive urine pregnancy test (βhCG) at screening or visit 1, are trying to become pregnant or are breastfeeding. 7. Subjects with active cancer within the previous 2 years, except treated basal cell carcinoma of the skin 8. Subjects who have taken any experimental drug within 30 days prior to enrollment or within 5 half-lives of the investigational drug –whichever is the longer period.

CONFIDENTIAL INFORMATION

The information in this study protocol is confidential. Any disclosure, copying or distribution of the information contained within is strictly prohibited without written consent from MonoSol Rx LLC.

	
However, subjects who have previously completed other MonoSol Rx sponsored ROSF clinical studies within the last 30 days prior to enrollment may be eligible for consideration for entry into this study.
 
9. Subjects with known history or presence of moderate or severe renal impairment as defined by a calculated creatinine clearance of ≤ 50 mL/minute10. Subjects currently taking riluzole with ALT levels greater than 5 times upper limit of normal or with evidence of clinical jaundice. (Riluzole should be discontinued in these patients.)11. Subjects who will be receiving riluzole for the first time who exhibit baseline elevations of several LFTs (especially elevated bilirubin). (These findings at baseline should preclude the use of Riluzole including ROSF).12. Use of potentially hepatotoxic drugs: (e.g., allopurinol, methyldopa, sulfasalazine).13. Subjects with clinically significant abnormal laboratory values in the judgment of the investigator14. Use of strong or moderate CYP1A2 inhibitors (e.g., ciprofloxacin, enoxacin, fluvoxamine, methoxsalen, mexiletine, thiabendazole, vemurafenib, zileuton) and CYP1A2 inducers (e.g. rifampin and barbiturates) in the previous 30 days before drug administration.15. Anything else that, in the opinion of the investigator, would place the subject at increased risk or preclude the subject's full compliance with or completion of the study16. Employee or immediate relative of an employee of the investigator, MonoSol Rx LLC, any of its affiliates or partners, or inVentiv Health.
--	--

CONFIDENTIAL INFORMATION

The information in this study protocol is confidential. Any disclosure, copying or distribution of the information contained within is strictly prohibited without written consent from MonoSol Rx LLC.

Assessments	
• Comprehensive/brief physical exam• Comprehensive/brief neurologic exam• ALS Functional Rating Scale – Revised (ALSFRS-R scale)• Functional Oral Intake Scale (Crary, 2005).• Eating Assessment Tool -10 (Belafsky, 2008)• Videofluoroscopic swallowing study (VFSS)• Penetration Aspiration Scale (PAS) (Rosenbek, 1999)• Adverse events• Clinical laboratory evaluation(s)• Urine Pregnancy Test (females of childbearing potential)• Vital Signs, Height and Weight• Medical history• Concomitant medication• Inclusion/exclusion criteria
-------------	---

Statistical Analysis

Primary Outcome:

The primary objective is to assess the effect of the ROSF formulation, if any, on swallowing safety in subjects with ALS. The null hypothesis is that there will be no difference between the PAS scores (i.e. swallowing safety) obtained before and after administration of the study medication.

The PAS scores obtained in swallow tests during VFSS 1-PAS (before ROSF) and VFSS 2-PAS (after ROSF) will be compared within each subject with the non-parametric Wilcoxon Signed-Rank Test. Alpha will be set at 0.05, two-tailed. Analysis across each swallowing trial will be performed, providing 12 bolus stimuli trials and approximately 35 swallows and PAS scores for each elicited swallow across testing within each participant (across various textures and swallowing complexities given that multiple swallows are typically elicited per bolus stimuli trial) to ensure a comprehensive exam across a variety of liquid volumes, textures and consistencies).

CONFIDENTIAL INFORMATION

The information in this study protocol is confidential. Any disclosure, copying or distribution of the information contained within is strictly prohibited without written consent from MonoSol Rx LLC.

Sample size was determined for a within-person design (repeated measures, same subjects in VFSS 1-PAS and VFSS 2-PAS) using G*Power Version 3.1.9.2, assuming a correlation = 0.6 across the two measurements. A sample size of n=25 would be able to detect at least a 1.0 point difference (two-tailed), effect size 0.6, in PAS scores from Test 1 and Test 2 with 80% power. It is anticipated that approximately 20% of recruited ALS subjects will grossly aspirate during VFSS 1-PAS and will not have a VFSS 2-PAS performed (for both safety reasons and also because Test 2 would not yield any useful data due to a ceiling effect). Therefore enrollment is planned for a total of 30 subjects to account for this potential.

Depending on the study enrollment rate, the Sponsor may elect to perform an interim analysis using available data from the subset of subjects who have completed the study at that time. The results of this interim analysis will be used only for internal planning and possibly for sharing with regulatory authorities. The results of the interim analysis will have absolutely no influence on the subsequent conduct of the study.

The following safety information will be included as descriptive summaries:

- Type, incidence, and severity of adverse events
- Physical and neurological examinations
- Vital signs (heart rate, blood pressure, rate, temperature), Height/Weight
- Clinical laboratory evaluation(s); see [Section 10.3.7 Laboratory Evaluations](#)
- Urine pregnancy test (females of childbearing potential)
- ALS Functional Rating Scale – Revised (ALSFRS-R) ([Cedarbaum, 1999](#))
- Functional Oral Intake Scale – FOIS ([Crary, 2005](#))
- Eating Assessment Tool 10 – (EAT-10) ([Belafsky, 2008](#))

CONFIDENTIAL INFORMATION

The information in this study protocol is confidential. Any disclosure, copying or distribution of the information contained within is strictly prohibited without written consent from MonoSol Rx LLC.

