10. STUDY PROCEDURES

10.1. Schedule of Activities

The schedule of study activities is presented in [Table 3](#).

Table 3 Schedule of Activities

Evaluation	Screening	Visit 1
Written Informed Consent	X	
Inclusion/Exclusion Review	X	X ^a
Documentation of Disease	X	
Record/Review Concomitant Medications	X	X ^a
Medical History/ Demographics	X	
Height and Weight	X	
Vital Signs – HR, BP, RR		X ^b
Vital Signs – HR, BP, RR and temperature	X	X ^a
Comprehensive Physical Exam	X	
Brief Physical Exam		X ^b
Neurological Examination	X	
Brief Neurological Exam		X ^b
Eating Assessment Tool-10 (EAT-10)	X	X ^a
Functional Oral Intake Scale (FOIS)	X	X ^a
ALS Functional Rating Scale - Revised (ALSFRS-R)	X	X ^a
Oral Examination	X	X ^c
VFSS 1 - Penetration-Aspiration Scale (pre-dose)		X
VFSS 2 - Penetration-Aspiration Scale (post-dose)		X
Clinical laboratory evaluation(s)hematology, chemistry, urinalysis) ^d	X	X ^b
Urine Pregnancy Test (females of childbearing potential)	X	X ^a
Adverse Event	X	X ^c
Dispense Study Drug (one dose)		X

^aBefore VFSS 1 procedure

^bAfter VFSS 2 procedure

^cBoth – before VFSS 1 procedure and after VFSS 2 procedure

^dSee [Section 10.3.7 Laboratory Evaluations](#)

CONFIDENTIAL INFORMATION

The information in this study protocol is confidential. Any disclosure, copying or distribution of the information contained within is strictly prohibited without written consent from MonoSol Rx LLC.

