10.2.2. On-Study/On-Intervention Evaluations/Procedures

10.2.2.1. Baseline (Day 0, Visit 1):

The baseline visit (Day 0, Visit 1) will include a single dose of study drug. It will be scheduled within 28 days after the screening visit. At this visit, inclusion/exclusion criteria and concomitant medications will be reviewed. Vital signs, brief physical and neurologic examination, as well as study questionnaires and testing will be performed as noted in [Table-3; Schedule of Activities](#).

The following documentation and procedures will be performed at Day 0 (Visit 1):

- Adverse event review (before VFSS 1 procedure and after VFSS2 procedure)
- Inclusion/exclusion assessment (before VFSS 1 procedure)
- Concomitant medications (before VFSS 1 procedure)
- Urine pregnancy test for females of childbearing potential (before VFSS 1 procedure)
- Vital signs HR, BP, RR and temperature (before VFSS 1 procedure)
- Vital Signs HR, BP, RR (after VFSS 2 procedure)
- Oral Exam (before VFSS 1 procedure and after VFSS 2 procedure)
- Videofluoroscopy Swallow Study 1 (VFSS 1; pre dose procedure)
- Administer study drug (one dose)
- Videofluoroscopy Swallow Study 2 (VFSS 2; post dose procedure)

CONFIDENTIAL INFORMATION

The information in this study protocol is confidential. Any disclosure, copying or distribution of the information contained within is strictly prohibited without written consent from MonoSol Rx LLC.

- Brief physical exam (after VFSS 2 procedure)
- Brief neurologic exam (after VFSS 2 procedure)
- Clinical laboratory evaluation(s) see [Section 10.3.7 Laboratory Evaluations \(after VFSS 2 procedure\)](#)

Videofluoroscopy Swallow Study (VFSS 1-PAS)

Subjects will undergo a standardized videofluoroscopic swallowing study (VFSS) for direct visualization of the swallowing process and any episodes of penetration or aspiration. The VFSS represents the gold standard swallowing exam to directly visualize swallowing and specifically aspiration during swallowing. After consent has been verified and screens completed, the patient will be seated and will complete a standardized bolus protocol that includes 12 bolus trial presentations in the following order:

1. 5ml thin liquid barium
2. 5ml thin liquid barium
3. 5ml thin liquid barium
4. Regular sip of thin liquid taken from a cup containing 60cc of thin liquid.
5. Consecutive cup sips of remaining thin liquid barium
6. Tablespoon of thin honey consistency barium
7. Tablespoon of thin honey consistency barium

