8. Tablespoon of thin honey consistency barium
9. Tablespoon of pudding consistency barium.
10. Tablespoon of pudding consistency barium.
11. Graham cracker with pudding-thick barium.
12. 13 mm barium tablet (EZ-Disk) with water.

A standard ‘bail out’ criteria used on all VFSS protocols in the Swallowing Systems Core laboratory will be utilized in this study. This represents a standard provision to avoid unnecessary risk to research subjects during VFSS exams and will include cessation of bolus presentations during a specific VFSS test (i.e. either VFSS 1 or VFSS 2) on the third episode of frank aspiration (material entering the airway below the level of the true vocal folds) or residue greater than 75% of either vallecular or pyriform housing that is unable to be cleared by the patient with prompting and strategies. The potential for this to occur is factored into the targeted enrollment of approximately 30 subjects in an effort to complete 25 subjects for the swallowing evaluation consistent with the sample size estimation ([Section 13.5.3; Power](#)).

The start time and finish time for the standardized bolus protocol will be recorded for both VFSS 1 and VFSS 2.

CONFIDENTIAL INFORMATION

The information in this study protocol is confidential. Any disclosure, copying or distribution of the information contained within is strictly prohibited without written consent from MonoSol Rx LLC.

Immediately following VFSS 1-PAS, the patient will then be administered ROSF on the dorsum of tongue along the median lingual sulcus, and the time of administration will be recorded ([Appendix B](#)). Following a three-minute time interval the investigator will confirm that the ROSF has dissolved and VFSS 2-PAS will be performed. If ROSF is not fully dissolved at 3 minutes, start of the second VFSS 2-PAS bolus protocol will be delayed until investigator confirms that ROSF is fully dissolved. The investigator should record whether or not ROSF is fully dissolved at 3 minutes after dosing. In the event that ROSF is not fully dissolved at 3 minutes, the investigator will record the time that it is confirmed that ROSF is fully dissolved.

Videofluoroscopy Swallow Study Test 2-PAS (VFSS 2-PAS)

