11.1. Adverse Experience Reporting and Follow Up

Subjects will be instructed to inform clinic personnel of any untoward medical symptoms and/or events that may arise during the course of the study. If an adverse event is experienced by a subject, then the subject will be questioned concerning symptoms that may have occurred after the administration of the study drug. The incidence, severity and duration of all AEs will be recorded according to the following scale:

Mild	Adverse event resulting in discomfort, but not sufficient to cause interference in normal daily activities
Moderate	Adverse event resulting in discomfort that is sufficient to cause interference in daily activities.
Severe	Adverse event resulting in discomfort causing an inability to carry out normal daily activities

Subjects who withdraw due to an adverse event will be followed whenever possible until resolution of the adverse event. It may be appropriate for the subject to return to the site 2 weeks after the subject is off study to evaluate for resolution of any adverse events and to receive further information about options for future clinical care. The Investigator will decide the course of action.

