1. INTRODUCTION

This statistical analysis plan (SAP) is intended to give a detailed description of the summaries and the analyses that will be generated for the present study by inVentiv Health Clinical. Analyses specified in this plan are based on Protocol 17MO1R-0012 Version 2.0, Amendment I, dated 18 October 2017. Safety and tolerability analyses will be described.

The original plan has changed as described below. Further details are documented in the remainder of this document. These changes will also be described in the clinical study report (CSR).

Top-line clinical results from the Videofluoroscopic Swallowing Study (VFSS) for the first 7 completed patients were presented to the Food and Drug Administration (FDA) on Sept 10 2018. At that time, two additional patients had been enrolled but had not yet undergone the VFSS. On Sept 12 2018, the FDA agreed with the Sponsor that due to the lack of any signal of detrimental effect on VFSS after one dose of study drug, the study would be terminated after the completion of 9 patients (the seven completed by Sept 10 and the two additional patients in screening at that time). In addition to the lack of signal of any harmful effect, the Agency and the Sponsor took into account the difficulty and hardship involved for these disabled patients in participating in the study, the potential risks of participation (including possible reaction to barium, potential for aspiration, and exposure to radiation), and the fact that the participating patients would derive no direct benefit for participation.

When applicable, all methodology and related processes will be conducted according to Standard Operating Procedures (SOPs) of InVentiv Health Clinical.

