6.5.1 Adverse Events

Treatment-emergent AE (TEAE)s will be defined as AEs that occur on or after the date and time of study drug administration, or those that first occur pre-dose but worsen in frequency or severity after study drug administration. TEAEs will be captured through the end of the study. TEAEs and non-TEAEs (those occurring prior to administration of study medication or that first occurred prior to study drug administration and did not worsen in frequency or severity) will be listed.

The MedDRA[®] dictionary version 19.1 will be used to classify all AEs reported during the study by SOC and PT.

The relationship of TEAEs to study drug will be classified according to the study protocol as unrelated, unlikely, possible, or probable. The severity of AEs will be rated according to the study protocol as: mild, moderate, or severe.

An SAE is any untoward medical occurrence that:

- results in death,
- is life-threatening,
- requires inpatient hospitalization or prolongation of existing hospitalization,
- results in persistent or significant disability/incapacity,

- is a congenital anomaly/birth defect

A significant AE will be defined as any event (other than those reported as serious) that necessitated an intervention, including withdrawal of treatment, or significant additional concomitant therapy.

Serious and significant AEs will be listed separately.

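### No adverse-event question is scheduled between VFSS 1 and film placement, so dating unvolunteered VFSS 1 symptoms rests on recall, and events caused by VFSS 2 are treatment-emergent by timing alone

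*Protocol*

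**What the plan says.** - The protocol synopsis (section 3), after describing VFSS 1: "Immediately following, subjects will be given a single dose of riluzole oral soluble film (ROSF) 50mg".
- Protocol 10.2.2.1 repeats the synopsis sequence: "Immediately following VFSS 1-PAS, the patient will then be administered ROSF on the dorsum of tongue along the median lingual sulcus". The time of administration is recorded. VFSS 2 follows after three minutes, or later if the film has not dissolved.
- Protocol 10.2.2.1 lists the Visit 1 procedures, including "Adverse event review (before VFSS 1 procedure and after VFSS2 procedure". Footnote c of Table 3 (10.1) gives the same two points: "before VFSS 1 procedure and after VFSS 2 procedure".
- Protocol 11.1 asks subjects to tell staff of untoward symptoms at any time. If an event is reported, "then the subject will be questioned concerning symptoms that may have occurred after the administration of the study drug".
- SAP 6.5.1 defines treatment-emergent events (TEAEs) as "AEs that occur on or after the date and time of study drug administration", plus pre-dose events that become more frequent or more severe after the dose. SAP 6.5 summarises TEAEs. For events that are not treatment-emergent, 6.5.1 mentions only a listing.
- Protocol 11.2 grades each event's relationship to the drug on four levels. None is a procedure or barium category.
- SAP 1 names procedure risks itself: "possible reaction to barium, potential for aspiration, and exposure to radiation".

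**The concern.** PAS is compared examination against examination in the same subject. AEs are not. VFSS 1, the dose and VFSS 2 all fall between two scheduled AE reviews, and both examinations can themselves cause cough, nausea or throat discomfort.

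Two consequences follow. First, an unvolunteered symptom that began in VFSS 1 is systematically asked about only after the film and the second series, so whether it preceded the dose must be remembered across a short, busy interval. The worsening rule has the same difficulty: it needs a pre-dose state to compare with, and no AE record is scheduled at that point. Second, a symptom caused by the second barium series enters the TEAE summary with no recall error at all, because the definition looks only at the dosing time.

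What is at stake is how the AE summary reads. With 9 subjects, one such event is 1/9 = 11% of the safety population.

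**Working it through.** **Order of events at Visit 1 (Protocol 10.1, 10.2.2.1)**

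1. AE review.
2. VFSS 1.
3. Film placed, time recorded.
4. Three minutes, or longer until dissolved.
5. VFSS 2.
6. AE review.

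No AE review lies between steps 2 and 3. Protocol 11.3 has symptoms reviewed before any subsequent dosing, but in a single-dose study that sets no review between VFSS 1 and the only dose.

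**How an event is then classified (SAP 6.5.1)**

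| Event | Class | Depends on recall? |
|---|---|---|
| Starts in VFSS 1, volunteered or observed, does not worsen | not a TEAE, listed | no |
| Starts in VFSS 1, elicited only after VFSS 2 | either, according to remembered onset or worsening | yes |
| New in VFSS 2, caused by barium or procedure | TEAE, summarised | no |

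**Subjects without VFSS 2.** Protocol 13.5.3 expects about 20% of recruits to aspirate grossly in VFSS 1 and have no VFSS 2. The only later AE review is tied to the end of VFSS 2, so the schedule gives them no AE question after VFSS 1. Any who are not dosed are also outside the safety population (SAP 5.1).

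**Illustrative size.** The plan has no figure of its own to reproduce here, because the documents give no procedure-event rate. I assume that each VFSS alone causes an event in a fraction r of subjects, that the film adds nothing, that subjects and examinations are independent, and that all 9 completers (SAP 6.2) have both examinations. The range for r is 5% to 20%.

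VFSS 2 only: expected subjects = 9r; P(at least one) = 1 − (1 − r)^9.

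- r = 0.05: 0.45 subjects; 1 − 0.95^9 = 0.37
- r = 0.10: 0.90 subjects; 1 − 0.90^9 = 0.61
- r = 0.20: 1.80 subjects; 1 − 0.80^9 = 0.87

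Upper bound, with every VFSS 1 event also mis-dated to after the dose: expected subjects = 9[1 − (1 − r)^2]; P(at least one) = 1 − (1 − r)^18.

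- r = 0.05: 0.88 subjects; 0.60
- r = 0.10: 1.71 subjects; 0.85
- r = 0.20: 3.24 subjects; 0.98

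**The case against.** The visit is supervised throughout. Staff run VFSS 1, place the film and confirm dissolution. Subjects may report symptoms at any time (11.1), the investigator monitors throughout (Protocol 11), and staff record all symptoms (11.3). AEs carry an onset time, the dosing time is recorded, and "The start time and finish time for the standardized bolus protocol will be recorded for both VFSS 1 and VFSS 2". The 11.1 questioning is a follow-up once an event is reported and does not limit what is collected. All of this stands, and it confines the recall problem to symptoms that are neither volunteered nor seen.

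Four stronger readings are tempting, and the documents do not support them:

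- That VFSS 1 events automatically become TEAEs. An event with a correctly recorded pre-dose onset that does not worsen stays non-treatment-emergent.
- That aspiration is mis-timed. It is recorded on video and scored swallow by swallow, separately for each examination (10.2.2.1, 13.5.1).
- That the relationship scale ignores other causes. Its possible, unlikely and unrelated grades all admit them, so a barium reaction can be graded unlikely or unrelated. It would still be a TEAE.
- That no film-free comparison exists. VFSS 1 is the same bolus series in the same subjects without the film; the AE summary simply does not use it.

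It can also be said that VFSS 1 is a poor control for AEs. That is right. VFSS 2 always comes second, barium accumulates, and the window from VFSS 1 to the dose is short, so delayed VFSS 1 effects fall into later intervals even with perfect timing. A time-based TEAE definition also errs towards attributing more to the drug. Finally, the table shells are in a separate document, so an interval display could exist there; SAP 6.5.1 specifies none.

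**Conclusion.** The point holds as a minor attribution weakness in a descriptive AE summary. The schedule and the TEAE definition support it directly. The VFSS 2 part needs no recall error; the VFSS 1 part is a risk in dating unvolunteered symptoms, and no more than that.

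The 37% to 87% range rests wholly on the assumed 5% to 20% rate. A reader might take 60% to 98% as the likely size, but that requires every VFSS 1 event to be mis-dated, which nothing in the documents suggests, so it serves only as an upper bound. Nor do the documents support reading the point as a threat to the PAS comparison, which uses separately recorded examinations.

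**What to change.** 1. In Protocol Table 3 and 10.2.2.1, add a brief AE question after VFSS 1 and before film placement, for any subject still to be studied. It gives the worsening rule a pre-dose record and also covers subjects who do not go on to VFSS 2. SAP 1 shows seven subjects complete and two awaiting VFSS at the time of the regulatory discussion, so at that stage it could reach two at most.
2. In SAP 6.5.1, show AEs by onset interval from the recorded times: VFSS 1 start to dosing; dosing to VFSS 2 start; VFSS 2 start to finish; after VFSS 2. Keep a separate row for uncertain onset. With 9 subjects, a listing that carries these interval flags is enough, and it works for all of them.
3. State that setting VFSS 1 beside VFSS 2 is a descriptive reference only, because order, cumulative barium and unequal observation windows are confounded with the film.

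The cost is one flagged listing from data already collected, mostly empty cells, and a short pause before dosing for any remaining subject.
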